4. Hypothesis and null hypothesis

This superiority trial hypothesises that the add-on integrated care intervention will lead to better outcomes across all measures compared to the TAU group.

The corresponding null hypothesis states that there is no significant difference in outcomes between the add-on integrated care intervention and the TAU group.

5. Randomisation and blinding

Participants will be randomly assigned to one of the two study arms using a centralised web-based system (REDCap) with varying block sizes. The allocation sequence is generated by a researcher not directly involved in the trial and is unavailable to the investigator, sponsor, and clinicians. Randomisation is stratified by the municipality of home address (Copenhagen, Gladsaxe, Lyngby-Taarbaek, Hillerød, Frederikssund).

Due to the nature of the intervention, blinding of participants and clinicians is not feasible.

All co-authors are blinded to group assignments until the primary analyses are completed. The actual randomisation group allocation is concealed, with values X and Y representing group assignments in the blinded dataset. The formula for converting the randomisation allocation variable will remain undisclosed until unblinding and is securely managed by a co-worker who will not be involved in conducting or assisting with any analyses.

6. Sample size

From study protocol¹:

"A minimal clinically important difference (MCID) score for the WHODAS 2.0 has not yet been established. It is difficult to find studies with populations comparable to the present study in the literature. Based on clinical experience and the sparse available literature, a conservative minimal clinically important difference was taken to be five scale points on WHODAS 2.0 12-item version, and within-groups SD was taken to be 10 scale points. With a power level of 80% and alpha of 0.05, we estimate a sample size of each group of 64 and a total of 128. The completion rate in the preceding randomised trials at the CTP was two thirds, and we, therefore, set the expected drop-out rate to 35% for this study. The investigators increased the number of patients included to 128 × (1/ (100%-35%)) and, consequently, estimated a total sample size of 197 patients. Inclusion stops when approximately 197 patients are included in the trial. In the case that an MCID for WHODAS 2.0 is established during the time frame of the trial, this will be considered in the analyses. For the secondary outcome measures with a Cohen's d of 0.5, we have 80% power to detect a change of 0.21 on HTQ, 3.03 on HDRS, 3.77 on HARS, 0.25 on HSCL, 3.0 on SDS, 8.0 on WHO-5, 4.05 on GAF-F, and 2.85 on GAF-S."

In 2022, the Danish Health Authority assessed the MCID for the WHODAS 2.0 12-item and chose a standardised mean difference (SMD) of 0.3^2 . Based on this, we will revise the MCID from 5 scale points to 3 scale points to align with the Danish Health Authority when interpreting our findings.

7. Confidence intervals and p-values

Two-sided 95% confidence intervals will be reported for all estimated effects.

A two-sided p-value of <0.05 will be considered statistically significant for outcomes.

8. Analysis populations

Intention-to-treat (ITT) population

All randomised participants will be included in the ITT analysis, which will be conducted according to their assigned groups, regardless of their adherence to the intervention.

Per-protocol (PP) population

The PP analysis will include participants who fulfil completer criteria as per protocol. Completer criteria include attending five MD sessions, 10 psychologist sessions, and, additionally, two intersectoral collaborative meetings for the intervention group.

9. Outcome measures

Outcome measures are collected pre- and post-treatment and are divided into primary, secondary, and explorative outcomes. Explorative outcomes are scales that are not yet validated in the study population. We also conduct a follow-up at 8 months after treatment, but the follow-up study is not included in this SAP (follow-up data will be analysed in a separate study).

Abbreviation	Scale Name	Туре	Measuring	Score reporting	Better score
Primary outcor	ne	•		•	·
WHODAS 2.0	World Health Organization Disability Assessment Schedule 2.0 (12-item)	Interview	Functioning	Total score 0-48	Lower
Secondary out	comes	•		•	
HDRS	Hamilton Depression Rating Scale (17-items)	Observer	Depression symptoms	Total score 0-52	Lower
HARS	Hamilton Anxiety Rating Scale	Observer	Anxiety symptoms	Total score 0-56	Lower
GAF-S	Global Assessment of Functioning - Symptoms	Observer	Global symptoms	Score 0-100	Higher
GAF-F	Global Assessment of Functioning - Functioning	Observer	Global functioning	Score 0-100	Higher
HTQ	Harvard Trauma Questionnaire (Part IV, 16 items)	Self-rating	PTSD Symptoms	Mean score 1-4	Lower
HSCL-25	Hopkins Symptom Checklist 25	Self-rating	Anxiety and depression symptoms	Mean score 1-4	Lower
WHO-5	World Health Organization Five Well- Being Index	Self-rating	Quality of life	Transformed scores 0-100	Higher
SDS	Sheehan Disability Scale	Self-rating	Functioning	Total score 0-30	Lower
Exploratory ou	tcomes				
PMLD	Post-Migration Living Difficulties Check List	Self-rating	Post-migration Stressors	Total count 0- 17*	Lower
EQ-5D-5L	European Quality of Life (5 Dimensions, 5 Levels)	Self-rating	Quality of Life	Utility score -0.757 to 1** EQ-VAS score 0- 100	Higher
CHAI	Consumer Health Activation Index	Self-rating	Patient activation	Transformed score 0-100	Higher

*Total count is calculated on number of positive items, defined as a minimum score of "serious". **Based in the Danish value set³

10. Statistical analyses

Baseline Characteristics

Descriptive statistics will summarise baseline demographic and clinical characteristics by group. Continuous variables will be presented as means and standard deviations, while categorical variables will be presented as frequencies and percentages. We will describe and compare the means and differences between the two intervention groups.

Primary Analysis

The primary analysis will compare the change in functioning scores (WHODAS 2.0) from pre- to posttreatment between the TAU and intervention group with adjustment for the corresponding baseline measures by ANCOVA/linear regression and with multiple imputations to handle missing data. The analysis will follow the ITT principle, including all randomised participants with available data.

Secondary and explorative analyses

Secondary outcomes will be analysed similarly using ANCOVA/linear regression.

11. Interim analyses

No interim analyses are performed.

12. Handling of missing data

The proportion and amount of missing data will be reported. Missing data will be addressed using multiple imputations, under the assumption that data is missing at random. Sensitivity analyses will be conducted to assess the robustness of the findings in relation to different missing data mechanisms (*see 14. Sensitivity analyses*).

13. Covariate adjustment

Analyses will be adjusted for the stratification variable and no other, complying with RCT analysis guidelines from the European Medicines Agency. For outcome variables, we will adjust for their corresponding baseline measure.

14. Sensitivity analyses

Sensitivity analyses will be conducted to assess the robustness of the primary results and will be reported as supplementary to the main analyses.

Baseline covariates found to be imbalanced between the intervention and TAU groups will be identified based on group comparisons and included as covariates in adjusted outcome analyses.

We will examine whether participants with missing post-treatment outcome data differ systematically from those with complete data by comparing baseline characteristics.

To explore the potential impact of missing data, outcomes will be calculated with all missing outcome data replaced with a value equalling the mean of the outcome variable ± 2 standard deviations.

We will conduct observed case analyses.

Additionally, we will conduct a PP analysis to evaluate the influence of adherence to the intervention. Results from the PP analysis will be compared with the ITT analysis to assess whether non-adherence may have affected the study outcomes.

15. Assumptions

To ensure the validity of the statistical models used in this study, the following assumptions will be tested:

- a) Normality of residuals
 Assumption: Model residuals should be approximately normally distributed.
 Control: Visual inspection using histograms and Q-Q plots of residuals.
 Formal test: Shapiro-Wilk test (if required).
- b) Homogeneity of variance (Homoscedasticity)
 Assumption: The variance of residuals should be consistent across groups.
 Control: Levene's test or Bartlett's test for equality of variance.
 Breusch-Pagan test to check for heteroscedasticity.
- *c)* Outliers and influential cases
 Assumption: No extreme outliers that unduly influence results.
 Control: Cook's distance and standardised residual plots to detect influential cases.

If statistical assumption checks indicate violations of normality or homoscedasticity, we will apply analyses of log transformation of outcome and Mann-Whitney U-test.

17. Software

All statistical analyses will be conducted using STATA version 18.

References

- 1. [name] *et al.* The effect of an integrated care intervention of multidisciplinary mental health treatment and employment services for trauma-affected refugees: study protocol for a randomised controlled trial. *Trials* **23**, (2022).
- 2. Danish Health Authority. Focused clinical question regarding National Clinical Recommendation on the use of mild tranquilizers. (2022).
- 3. Jensen, C. E. *et al.* The Danish EQ-5D-5L Value Set: A Hybrid Model Using cTTO and DCE Data. *Appl Health Econ Health Policy* **19**, 579 (2021).

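### Does lowering the WHODAS 2.0 MCID from 5 to 3 points leave the sample-size section inconsistent with its cited standardised difference and its 80% power?

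*SAP*

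**What the plan says.** Section 6 of the SAP first reproduces the protocol's sample-size paragraph. There the important difference on the primary outcome "was taken to be five scale points on WHODAS 2.0 12-item version, and within-groups SD was taken to be 10 scale points", and the result is "With a power level of 80% and alpha of 0.05, we estimate a sample size of each group of 64 and a total of 128", raised to 197 for 35% drop-out. The same paragraph foresees that an MCID might be established while the trial runs and would then be taken into account.

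The SAP's own text follows. It reports that the Danish Health Authority "chose a standardised mean difference (SMD) of 0.3" and concludes that "we will revise the MCID from 5 scale points to 3 scale points to align with the Danish Health Authority when interpreting our findings".

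Two other sections bear on how a result is read. Section 7 promises two-sided 95% confidence intervals for all effects and adds: "A two-sided p-value of <0.05 will be considered statistically significant for outcomes". Section 4 says: "The corresponding null hypothesis states that there is no significant difference in outcomes between the add-on integrated care intervention and the TAU group".

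**The concern.** The authority's threshold is on a standardised scale and the SAP's is in raw points. They coincide at one SD only, and the SAP does not name that SD beside the conversion. If the observed SD turned out smaller or larger than 10, an estimate could meet one threshold and miss the other.

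The 80% power also stands directly above a new and smaller MCID. A quick reader could carry it over to 3 points, where it does not apply.

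Finally, the null hypothesis in section 4 describes a test result rather than a true difference. Read literally, any p-value above 0.05 would satisfy it, even when the confidence interval still contains a 3-point benefit. At stake would be the wording of the primary conclusion: a trial that had not excluded a difference it calls important might be reported as showing none.

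**Working it through.** **Inputs from the SAP:** difference 5 points, SD 10, power 80%, drop-out 35%, 197 randomised, standardised difference 0.3 and revised MCID 3 points (section 6); two-sided 5% level (section 7); adjustment for baseline by ANCOVA (sections 10 and 13). **Assumed, because the SAP does not give it:** the baseline-to-post correlation *r*, taken from 0 to 0.7.

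**1. The plan's own figures.** With d = 5/10 = 0.5, a two-sided two-sample t-test at 5% with 80% power needs 63.8, so 64 per arm; power at 64 is 80.1%. Then 128/0.65 = 196.9, so 197. All reproduce.

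**2. The conversion.** 0.3 × 10 = 3.0 points, which agrees with the section's planning SD. At other SDs (assumed), 0.3 × SD is 2.1 points at SD 7, 2.4 at SD 8 and 3.6 at SD 12.

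**3. Power at 3 points.** SE = 10 × √(1 − r²) × √(2/64), with power from the noncentral t distribution.

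| r | SE | 95% CI half-width | Power at 3 points, 64 per arm |
|---|---|---|---|
| 0 | 1.768 | 3.50 | 39% |
| 0.5 | 1.531 | 3.03 | 49% |
| 0.6 | 1.414 | 2.80 | 56% |
| 0.7 | 1.262 | 2.50 | 65% |

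Power of 80% would need r = 0.8: the residual SD is then 10 × √(1 − 0.64) = 6, and 3/6 = 0.5.

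**4. Sensitivity to the number of outcomes.** The 64 per arm supposes that 35% of participants give no post-treatment outcome. With none missing there would be about 197/2 = 98 per arm, and power at 3 points would be 55% (r = 0), 67% (r = 0.5) and 83% (r = 0.7).

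**5. Chance that the interval still contains a 3-point benefit when the true effect is zero.** 1 − Φ((3 − half-width)/SE). For r = 0 this is 1 − Φ((3 − 3.50)/1.768) = 61%; for r = 0.5, 0.6 and 0.7 it is 51%, 44% and 35%. Each is 100% minus the power in step 3, so this is the same fact restated and not a second consequence.

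**6. Disagreement between the two scales.** If the true difference is 3 points, the chance that the estimate falls between 0.3 × SD and 3 is, for SD 8 and r = 0 (SE = 8 × √(2/64) = 1.414), Φ(0.6/1.414) − 0.5 = 16%; with r = 0.5 it is 19%. The same calculation gives 27% to 30% at SD 7 and 11% to 13% at SD 12. These rates set the SAP's threshold against one that the SAP does not use.

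**The case for a change.** The best case for a change runs as follows. The SAP itself introduces the 3-point threshold, gives interpretation as its purpose, and then does not say how an estimate or interval is read against it. Matching a standardised difference and fixing a raw number are different criteria once the SD departs from 10, and the choice between them should be made before unblinding. On the SAP's own SD and completer numbers, the design has well under 80% power at the new MCID. A few sentences would settle all of this at almost no cost.

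Part of that stands. The conversion SD is not labelled, power at 3 points is not given, and the null hypothesis is loosely worded.

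The rest does not carry. The choice between scales has been made: the SAP names 3 scale points, and a fixed raw threshold does not move with the observed SD. The power shortfall contradicts nothing, because the SAP never claims 80% at 3 points. Its size also depends on an unknown correlation and on the number of outcomes obtained. The 39% figure assumes that baseline explains nothing, although the planned analysis adjusts for it. The 35% drop-out was derived from completion rates in earlier trials, and section 8 defines completers by sessions attended, so some non-completers may still provide an outcome. Multiple imputation would not restore all the lost information, so realised power probably lies between the 64 and 98 per arm cases.

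**Conclusion.** No change to the plan follows. The stated figures of 64, 128, 197 and 80% are correct for the 5-point difference to which they are tied, and 3 points is 0.3 times the SD given in the same section. The revision came after the design calculation, was foreseen in the quoted protocol text, and is confined to interpretation.

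Power at 3 points is about 39% to 65% with 64 outcomes per arm and 55% to 83% with 98, for SD 10 and an assumed r of 0 to 0.7. That is a fact about the design. Stating it would not alter the test, the estimate, the threshold or the sample size.

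The protection that matters is already present. A 95% confidence interval will be reported and 3 points is named in advance, so a reader can see directly whether a 3-point benefit has been excluded. Nothing in the SAP commits the authors to reading non-significance as no effect. The wording of the null hypothesis in section 4 is a clerical slip: the planned comparison plainly tests a true difference of zero. The authors may wish to label the conversion and note that 80% refers to 5 points, but a competent analyst would read the section that way already.

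### Does the available-data qualifier in SAP section 10 leave the primary analysis set undefined?

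*SAP*

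**What the plan says.** Section 8 defines the ITT population without any condition on data: "All randomised participants will be included in the ITT analysis", by assigned group and whatever the adherence.

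Section 10 (Primary Analysis) describes an ANCOVA or linear regression of WHODAS 2.0, adjusted for baseline, "with multiple imputations to handle missing data". The next sentence reads: "The analysis will follow the ITT principle, including all randomised participants with available data". Which data must be available (baseline, post-treatment, either or any) is not stated there or elsewhere.

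Section 12 sets the general rule: "Missing data will be addressed using multiple imputations, under the assumption that data is missing at random". It is not limited to post-treatment scores.

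Section 14 lists analyses that "will be reported as supplementary to the main analyses". Among them are an observed-case analysis ("We will conduct observed case analyses") and an extreme-value analysis "with all missing outcome data replaced with a value equalling the mean of the outcome variable" plus or minus 2 standard deviations.

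**The concern.** The SAP describes the primary analysis set twice, and the two statements differ. Section 8 takes everyone randomised, while section 10 appends a condition that it does not define. Read literally, the condition could mean that only participants with a measured post-treatment WHODAS count.

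Three parts of the plan would then stop working. There would be no primary outcome left to impute. The primary analysis would become the observed-case analysis that section 14 treats as supplementary. Comparing the two would then say nothing about the effect of missing data. With drop-out planned at 35%, this could concern about a third of the participants, and the set behind the primary result should not be left to the analyst.

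**Working it through.** **1. The plan's own figures.** Section 6 gives a difference of 5 points, SD 10, 80% power and alpha 0.05, and section 7 makes the test two-sided. The two-sample t-test calculation gives 63.77 per group, rounded up to 64, so 128 in total (power 0.801 at 64 per group). Inflation for 35% drop-out gives 128 / (1 − 0.35) = 196.9, rounded up to 197. Both stated figures reproduce.

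**2. How many participants could depend on the phrase.** If every planned drop-out lacks the post-treatment score:
- missing: 197 × 0.35 = 68.95, about 69
- observed: 197 × 0.65 = 128.05, about 128

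This is a ceiling. The 35% comes from a completion rate in earlier trials, and section 8 defines completers by sessions attended, so a non-completer may still be measured. At an assumed 10% or 20% missing, the number is 19.7 or 39.4, about 20 or 39.

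**3. Each reading set against the rest of the SAP.**

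| Data that must be available | Analysed at 35% missing | Section 8 (all randomised) | Imputation in sections 10 and 12 | Separate observed-case analysis in section 14 |
|---|---|---|---|---|
| Post-treatment WHODAS | about 128 | contradicted | no outcome left to impute | duplicates the primary analysis |
| Baseline WHODAS | 197 less those without a baseline score (number not given) | nearly met | works | distinct |
| Any data | up to 197 | met, or nearly so | works | distinct |

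Only the first reading does harm. It conflicts with section 8, with the preceding sentence of section 10, with section 12 and with the list in section 14. The other two fit the document, and they differ only in participants without a baseline score, whom section 12's general rule on missing data can cover.

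**4. What the harmful reading would do to the estimate.** Suppose the imputation model holds only the terms of the analysis model: arm, baseline WHODAS and municipality. A participant without the single post-treatment score then adds no information on how that score depends on those terms. Imputation tends to the complete-case ANCOVA as the number of imputations grows.

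A simulation shows the size. Inputs from the SAP: N = 197, SD 10 and five municipalities. Assumed: municipalities equally likely, baseline-post correlation 0.5, no treatment effect, 35% missing completely at random, 50 imputations, 4,000 trials.
- Approximate complete-case standard error by hand: residual SD 10 × √(1 − 0.5²) = 8.66, and 8.66 × √(2/64) = 1.53. The simulation, which also estimates the covariate effects, gives 1.56.
- Standard error with imputation from the same covariates: 1.58.
- Imputation minus complete-case estimate: mean 0.00, SD 0.14.

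That SD is noise from using a finite number of imputations. The between-imputation variance is roughly 0.35 × 1.56² = 0.85, and √(0.85/50) = 0.13. A second run with 30 imputations and 1,500 trials gave mean 0.01 and SD 0.17, where √(0.85/30) = 0.17. At 10% and 20% missing (50 imputations), the SD was 0.06 and 0.09.

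**The case for a change.** The strongest case for a change is that clear intent does not make two sentences agree, and that deleting three words costs nothing. This stands as an editorial remark. The qualifier is undefined and section 8 does not contain it. The coded group labels in section 5 limit any choice by direction of effect, but they do not define a set.

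A second argument is that the two readings would part if the imputation model contained further variables, such as other baseline scales or session counts, so that the phrase could matter after all. That is possible. Section 13 ("Analyses will be adjusted for the stratification variable and no other", apart from each outcome's own baseline) governs the analysis model and does not bar auxiliary variables from the imputation. But the size rests on assumptions for which the SAP offers no source:
- If missingness depends on such a variable in one arm only (odds ratio 1.65 to 2.7 per SD, partial correlation with the outcome 0.3 to 0.5), complete-case bias at 35% missing is about 0.5 to 1.4 points. Imputation with the variable removes nearly all of it.
- If the dependence is the same in both arms, the bias is at most 0.04 points, which is simulation error.
- The gain in precision is about nil at a partial correlation of 0.2 to 0.3 (standard error 1.573 against 1.563 complete-case, and 1.554 against 1.559). It becomes a small loss when the variable strongly predicts missingness (1.574 against 1.550).

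This argument concerns which variables to impute from, a detail the SAP leaves open and does not misstate. Deleting the phrase in section 10 would change none of these figures.

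**Conclusion.** The wording is loose, but the plan is not defective on this point. Sections 8, 10, 12 and 14 read together fix the primary analysis as multiple imputation for all randomised participants, with observed-case analysis supplementary. An analyst following the document would arrive there without further instruction.

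The ceiling of 69 of 197 requires a reading that four places in the SAP exclude, and it also requires every drop-out to lack a score. Even on that reading, the estimate would not shift on average from one imputed on the analysis covariates alone: 0.00 points on average, against the 3-point difference that section 6 uses for interpretation. That comparison rests on the assumed correlation of 0.5, on outcomes missing completely at random, and on complete baseline scores. The SAP does not say how many baseline scores might be missing, but its missing-data rule is general enough to include them.

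No bias or altered conclusion has been shown for this trial. Defining or dropping the phrase would tidy the text without changing what is analysed, so no change to the plan follows.

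### Section 14 chooses covariates for a supplementary analysis by observed baseline imbalance, which randomisation makes a matter of chance, and states no candidates, cut-off or time of selection (minor)

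*SAP*

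**What the plan says.** Section 14 (Sensitivity analyses) sets the rule for its covariate-adjusted models: "Baseline covariates found to be imbalanced between the intervention and TAU groups will be identified based on group comparisons and included as covariates". The same section says that its analyses "will be reported as supplementary to the main analyses".

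Section 13 (Covariate adjustment) fixes the main model: "Analyses will be adjusted for the stratification variable and no other", followed by "For outcome variables, we will adjust for their corresponding baseline measure". Municipality and the outcome's own baseline score are therefore always in the model.

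No other section completes the Section 14 rule:
- Section 10 (Baseline Characteristics) says "Descriptive statistics will summarise baseline demographic and clinical characteristics by group" and that means and differences will be compared. It names no test or threshold.
- Section 7 gives a two-sided 0.05 level, but for outcomes.
- Section 5 describes central web-based randomisation, stratified by municipality, with coded groups: "The actual randomisation group allocation is concealed, with values X and Y representing group assignments in the blinded dataset". It adds: "All co-authors are blinded to group assignments until the primary analyses are completed". It does not say when covariates are selected.

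**The concern.** There are two separate weaknesses.

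1. **The selection criterion is the wrong property.** A covariate is worth adjusting for if it predicts the outcome. Under concealed randomisation, the size of a baseline difference among all randomised participants is chance and carries no information about prediction. A strongly prognostic variable is as likely to be left out as an irrelevant one.
2. **The rule is open.** Without candidates, a cut-off or a time of selection, two analysts following the SAP can fit different models to the same data. The X/Y coding limits the discretion but does not remove it. The size of an imbalance is visible without knowing which arm is which, and selection could also take place after the primary analyses, when the co-authors' blinding ends.

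What is at stake is the value of one robustness check: whether it can be reproduced from the SAP, and whether its standard error is right.

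**Working it through.** **Inputs from the SAP.** 197 participants, 1:1 allocation (Sections 3 and 6), taken as 98 and 99. Planned completers 64 per group, SD 10 WHODAS points, revised minimal important difference 3 points (Section 6). Section 9 says "Outcome measures are collected pre- and post-treatment and are divided into primary, secondary, and explorative outcomes". Besides WHODAS its table gives 12 baseline scores: eight secondary scales, PMLD, EQ-5D-5L utility, EQ-VAS and CHAI.

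**The plan's own figures.** A two-sample t-test with difference 5, SD 10, two-sided 0.05 and 80% power needs 63.77, so 64 per group and 128 in total. 128/0.65 = 196.9, so 197. These agree with Section 6 and are not in dispute.

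**Step 1. Chance that a given covariate enters.**
- Standard error of an SMD = √(1/98 + 1/99) = 0.1425.
- p<0.05 corresponds to |SMD| > 1.96 × 0.1425 = 0.279. Probability 0.050, so omitted in 95% of trials.
- |SMD| > 0.2: z = 0.2/0.1425 = 1.40. Probability 0.160, so omitted in 84%.
- |SMD| > 0.1: z = 0.1/0.1425 = 0.70. Probability 0.483, so omitted in 52%.

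None of this needs an assumption about prognosis. If all 12 scores are candidates, the expected number entering by chance is 12 × 0.050 = 0.6, 12 × 0.160 = 1.9 or 12 × 0.483 = 5.8.

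**Step 2. How often two common cut-offs give different models.** The p<0.05 and SMD>0.2 rules disagree on a covariate when its SMD lies between 0.2 and 0.279: 0.160 − 0.050 = 0.110. With k independent candidates the models differ with probability 1 − (1 − 0.110)^k.

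| Candidates (assumed) | Correlation | Different model |
|---|---|---|
| 5 | 0 | 44% |
| 12 | 0 | 75% |
| 12 | 0.5 | 66% |
| 12 | 0.7 | 54% |

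The correlated rows come from 400,000 random draws.

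**Step 3. Effect on the standard error and test, under assumed prognosis.** The SAP gives no prognostic strengths, so these are assumptions. There are 15 candidates (the 12 scores and 3 demographic variables), three of them prognostic and explaining 4 to 39% of the variance left after baseline WHODAS. Municipality and baseline WHODAS are always in the model. Six scenarios were run, with 60,000 trials each under no treatment effect. Data are complete, whereas the SAP plans multiple imputation.

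| Analysis | Reported SE against true sampling SD | Type I error |
|---|---|---|
| p<0.05 rule, all 197 | +0.8 to +5.8% | 3.7–4.9% |
| p<0.05 rule, 64 per arm | −0.1 to +3.0% | 4.3–4.9% |
| SMD>0.2 rule, all 197 | +1.0 to +8.2% | 3.4–4.8% |
| Prespecified three covariates | −0.7 to +0.5% | 4.7–5.1% |
| p<0.05 rule, no covariate prognostic | −0.4% | 5.1% |

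Monte Carlo error is about 0.3% on the SE ratio and 0.09 percentage points on type I error. The excess arises because a prognostic covariate is left out exactly when its imbalance is small. The estimate then varies less than the standard error reported without that covariate implies.

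Estimates under the two cut-offs differed by a median of 0.12 to 0.18 WHODAS points (90th percentile 0.40 to 0.96), against a standard error of about 1.0 to 1.6 and an important difference of 3.

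**Step 4. Price of a fixed list that turns out useless.** The main model has 7 coefficients (intercept, arm, baseline score, four for municipality). Adding three irrelevant covariates multiplies the standard error by about √(190/187) = 1.008 with 197 participants and √(121/118) = 1.013 with 128.

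**The case against.** The strongest reply is that little depends on this. Section 13 fixes the primary model, the affected analysis is labelled supplementary, and the typical shift between cut-offs is a small fraction of a standard error. That stands, and it is why the point is minor.

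A second reply is that asking whether the result survives adjustment for visible imbalances is a legitimate robustness question. A fixed list answers a different one, and naming candidates and a cut-off would already make the model reproducible. This stands in part: a completed imbalance rule is defensible as an extra check. It would still select on chance, however. With a stated SMD>0.2 cut-off the standard error remains 1 to 8% too large under the assumptions above.

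A third reply is that the SE and type I figures depend on assumed prognosis and complete data, and the 75% on twelve independent candidates. That is correct. With irrelevant covariates there is no distortion, and with five candidates the figure is 44%.

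A reader might infer more than the SAP supports:
- **That Sections 13 and 14 contradict each other.** The words "Analyses will be adjusted for the stratification variable and no other" do read as covering every analysis, but Section 14 marks its own as supplementary. This is loose wording.
- **That the rule biases the trial or inflates false positives.** Selection does not use the outcome, so averaged over randomisations there is no bias, and any error in the test is towards caution.
- **That a fixed list would gain power, or that particular scales belong on it.** The SAP gives no prognostic strengths and does not say which measures predict the outcome.

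**Conclusion.** The point holds as a minor, inexpensive improvement. Section 14 selects covariates on a property that randomisation makes uninformative, and leaves the candidates, cut-off and time of selection unstated. The omission rates of 95%, 84% and 52% follow from the sample size alone. The disagreement between cut-offs, 44 to 75% for five to twelve independent candidates and less if they are correlated, rests on an assumed number of candidates. The standard-error excess of roughly 0 to 8% applies only if the covariates are prognostic. The primary analysis and its conclusion are not affected.

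**What to change.** **Section 14.** Replace the sentence with:

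*A sensitivity analysis will additionally adjust for a short list of baseline measures, chosen by the sponsor for their expected relation to the outcome, fixed and dated before unblinding and used whatever the observed balance. Baseline differences will be described but will not select covariates; any adjustment for an unlisted variable will be labelled post hoc.*

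If the sponsor wishes to keep an imbalance-based check, the SAP should state the candidates, the cut-off and the time of selection (before unblinding), and label it secondary to the fixed-list analysis. That cures reproducibility only.

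**Section 13 (optional wording).** Say that the restriction to the stratification variable and the corresponding baseline measure applies to the main analyses.

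**Cost.** The change is to SAP text only. If none of three listed covariates is prognostic, the standard error of this check rises by about 0.8% with 197 participants and 1.3% with 64 per arm. The sponsor must justify the list, and an imbalanced variable that is not on it gets only a post hoc adjustment. The SAP does not say whether unblinding has occurred, so the list should carry a date relative to it.
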